With our primary outcome we aim to capture pain that interferes with their everyday lives and collect the location of pain. The patient characteristics (exposures) are based on results from our systematic review(14), used in other studies (when including references).

The specific wording in the outcomes and throughout the questionnaire has been pilot tested among similar aged kids and adolescents.

Our secondary outcomes highlight the development or potential aggravated psychological and social factors related to musculoskeletal pain at follow-up.

Primary outcome

1) MSK pain influence

Q: Have you experienced pain in the past two weeks that have lead you to not being able to participate in play in the school yard or sparetime activities (ex. football or other sparetime activity)(38)?

If yes, we ask them to draw the area where they have experienced this pain with the following question:

Q: Draw on your body the areas you have had pain during the past two weeks (39).

These two questions will form our primary outcome and will be collected at all endpoints.

Secondary outcomes

1) Problemfilled MSK pain.

*Q: Draw a circle around the area of your body, where you have had the **most** problems with pain. You may only draw **one** circle.*

2) Pain intensity depicted on Faces Pain Scale Revised (FPS-R) or a 10 cm VAS scale for 8-11 and 12-19 year olds respectively (9).

Exposures

3) Self-reported anxiety.

Q: "Do you feel anxious"?

4) Self-reported depression (16).

Q: "Do you feel depressed"?

5) Self-reported low self-esteem (16).

Q: "Do you think that you have low self-esteem"?

6) Duration of troublesome pain episode (40, 41).

Q: "How long does a pain episode usually last"? (see appendix 1 and 2 for the Q in full length).

7) Frequency of troublesome pain episode (10, 42, 43).

Q: "How often do have a pain episode"? (see appendix 1 and 2 for the Q in full length).

8) Nervousness (41).

Q: "How often do you feel nervous"? (see appendix 1 and 2 for the Q in full length).

9) Higher disability index (12, 44).

Q's with yes/no answers:

1. is it difficult to fall asleep because of pain?

2. is it difficult to sit during a lesson?

3. does your pain disturb a walk longer than 1km?

4. does your pain disturb your physical exercise?

5. does your pain disturb your hobbies?

10) Higher HFAQ level (40).

Q: "Does your pain make any of the following activities difficult"?

1. reaching up to get a book from a high shelf

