2. carrying your school bag to school

3. sitting on a school chair for a 45 min. lesson

4. standing in a queue for 10 min.

5. sitting up in bed from a lying position

6. bending down to put your socks on

7. standing up from an armchair at home

8. running fast to catch a bus

9. sport activities at school

11) Tired during the day (42, 45).

Sample-size

The sample-size in this study was determined using the two following rationales: 1) a sample-size large enough to test and replicate the analyses from previous studies on. Given the prior odds (0.5, 1, 2) of follow-up MSK pain for patients, using estimates for the prognostic factors female sex, high disability index, multisite pain, and maximum HFAQ from our systematic review(14). We gained an estimate of P-values according to sample size, for all factors individually (Appendix 8). Sample size of 500 patients, would result in an estimate of P-values below 0.05 for all prognostic factors and 2) investigate a range of new prognostic factors related to the sparsely investigated ethnicity and socioeconomic status. As no one has yet tested any of these potential important prognostic factors, and never in a general practice setting, we decided on 500 subjects. The 500 subjects was decided based on 250 cases (we assume 50% will continue to experience pain at our primary follow-up time) giving approximately 125 cases per prognostic factor (500/number of prognostic factors). The results from this analysis will be considered as explorative as no studies have previously been conducted in a general practice setting. Again, assuming 50% has pain at follow-up and 20 events for each to be tested factor are needed. The model should allow for 10-15 variables in a multivariable logistic regression analysis. This would lead to a sample size of 480. Assumed, 5% is lost to follow-up and we have a sample-size of 504 included participants. Given the high prevalence of MSK pain at follow-up, this sample-size is feasible to include.

Questionnaires

We use three questionnaires in data collection of patient and parent characteristics: participant baseline questionnaire (Part-Quest-base) (Appendix 1), participant follow-up questionnaire (Part-Quest-follow-up) (Appendix 2), and the parent questionnaire (Pare-Quest) (Appendix 3).

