Appendix 1: Participant Baseline Questionnaire (Part-Quest-baseline)

25. Do you expect to be free of your current pain in the future?

- o Yes, in the near future o Yes, in the long term future o No

26. Why did you come to your doctor today? You may choose more than one answer with circles.

- o I want my pain to stop
 o I am worried about the cause of my pain
 o My family made me come
 o I have a personal problem
 o Because of my pain, I can't use my body as I used to

27. Do you take painkillers, and what do you take? (50)

- o Yes, I take _____ .
 If yes, how often do you take them? _____
 o Yes, I take painkillers, but don't remember the name
 o No, I don't take painkillers

28. Do you expect your doctor to give you medication for your pain?

- o Yes, I would like that
 o No

29. If you have a job, how would you generally describe your physical activity in your job? (56) Please choose one.

- o Mostly sedentary work that does not require physical exertion
 o Mostly standing or walking work, which otherwise does not require physical exertion
 o Standing or walking work with some lifting or carrying work
 o Heavy or fast work which is physically strenuous
 o I don't have a job
 o I don't know

In the following last questions mark "x" in yes or no

[figure not shown]
[figure not shown]
	Yes	No
Is your pain radiating to your legs or arms(40)?		
Do you feel anxious(57)?		
Do you think that you have low self-esteem(57)?		
Do you believe in God?		
Is it difficult to fall asleep because of pain(44)?		
Is it difficult to sit during a lesson(44)?		
Does your pain disturb a walk longer than 1 km(44)?		
Does your pain disturb your physical exercise(44)?		
Does your pain disturb your hobbies(44)?		
Do you have pain outside school hours?		
Are you tired during the day(16)?		
Do you feel depressed(44, 57)?		

Does your pain make any of the following activities difficult(40)?	Yes	No
-reaching up to get a book from a high shelf		
-carrying your school bag to school		
-sitting on a school chair for a 45 min. lesson		
-standing in a queue for 10 min		
-sitting up in bed from a lying position		
-bending down to put your socks on		
-standing up from an armchair at home		
-running fast to catch a bus		
-sport activities at school		

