Appendix 2: Participant follow-up Questionnaire (Part-Quest-Follow-up)

11. What is the cause for your current MSK pain (ex. a fall, a hit or other)? (If you are familiar with it)

12. How long does a pain episode usually last?

- Less than 3 hours
- Less than 24 hours
- 1-7 days
- Longer than 7 days

13. How often do you have a pain episode?

- I don't have breaks from the pain
- At least once a week
- Less than once a week

14. How often do you feel nervous?

- Often/sometimes
- Seldom/never

15. How large a part of your friends have immigrant background?

- None
- Almost none
- Almost all
- All

16. Outside school hours, how many hours a day do you spend watching TV/tablet/mobile phone/computer or do other activities when mostly sitting down? _____ hours/day

17. Are you physical active besides school hours?

- Yes - how many times per week are you physical active besides mandatory physical education during school hours? _____
- No

18. Do you smoke cigarettes?

- Yes - how many cigarettes a day? less than 1 1-4 5-9 more than 9
- No

19. Do you expect to be pain free in the future?

- Yes, in the near future
- Yes, in the long term future
- No

20. Why did you come to your doctor today? You may choose more than one answer with circles.

- I want my pain to stop
- I am worried about the cause of my pain
- My family made me come
- I have a personal problem
- Because of my pain, I can't use my body as I used to

21. Do you expect your doctor to give you medication for your pain?

- Yes, I would like that
- No, I don't think so
- I don't know

22. If you have a job, what do you do _____ and how many hours do you work on a weekly basis? _____

In the following last questions mark "x" in either yes or no

Does your pain make any of the following activities difficult?	Yes	No
-reaching up to get a book from a high shelf		

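### Four school-only items in the HFAQ and disability index have no not-applicable answer, so both baseline exposures may be under-scored in participants out of school

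*Protocol*

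**What the plan says.** The inclusion criteria in the Protocol are an age of 8 to 19 years and self-reported musculoskeletal pain. School attendance is not required, and a separate consent declaration covers participants aged 18 and 19.

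Under Exposures, item 9 is the disability index (five yes/no questions) and item 10 is the HFAQ level (nine activities). Three HFAQ activities belong to school: "carrying your school bag to school", "sitting on a school chair for a 45 min. lesson" and "sport activities at school". One disability-index question does too: "is it difficult to sit during a lesson". In Appendices 1 and 2 the answer columns for these items are Yes and No only.

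Both participant forms foresee paid work. The baseline form asks "If you have a job, how would you generally describe your physical activity in your job", with options up to strenuous work and an option for having no job. The follow-up form asks "If you have a job, what do you do" and for weekly hours. Neither participant form, nor the parent form in Appendix 3, asks whether the participant goes to school.

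The Sample-size section gives two rationales. The first refers to estimates for "female sex, high disability index, multisite pain, and maximum HFAQ from our systematic review".

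**The concern.** A participant who is not at school has no fitting answer to the four items. No will be read as no difficulty, and a blank makes the score incomplete. Either way the recorded disability is lower than that of a pupil with the same limitation. The error would fall mostly on older participants and follow school status. It is plausibly also tied to socioeconomic status, which the study wants to examine.

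The forms themselves create the gap. If school status is not recorded, a later analysis plan cannot separate an activity that was not difficult from one that did not apply. The reference list suggests where the mismatch arises: by their titles, the study cited for the HFAQ concerned schoolchildren, and those cited for the disability index concerned preadolescents. The protocol applies the items up to age 19.

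**Working it through.** **The plan's own figure.** Inputs from the Sample-size section are 20 events per factor, 50% with pain at follow-up and 5% loss. With 12 factors (inside the stated 10 to 15), 12 × 20 = 240 events; 240 / 0.50 = 480; 480 × 1.05 = 504. The figure is reproduced, and no HFAQ or disability-index score enters it.

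**Ceiling on the scores.** This assumes No or blank on the school items, with a blank counted as zero.
- HFAQ: 9 − 3 = 6, and 6/9 = 67% of the scale.
- Disability index: 5 − 1 = 4, and 4/5 = 80% of the scale.

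**Share that could be affected.** Ages 8 to 19 are 19 − 8 + 1 = 12 year-groups. Ages 18 and 19 are 2/12 = 17%. That ceiling is reached only if recruitment is equal by year of age and everyone of those ages is out of school. Adding ages 16 and 17 gives 4/12 = 33%, again only a ceiling. The documents give no share out of school.

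**Illustration of the consequence.** The documents give no odds ratio, prevalence or cut-off for maximum HFAQ, so every input here is an assumption:
- N = 480, risk 50% in the unexposed, two-sided alpha 0.05, comparison of two proportions.
- Maximum means all nine items.
- A share f is truly at maximum, equally in and out of school.
- A share s is out of school and is never recorded as maximum.
- The odds ratio is 1.78 (borrowed from sex in Appendix 5) or 2.5 (chosen).

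Formulas:
- Risk in the truly exposed: p1 = OR/(1 + OR).
- Number recorded as exposed: n1 = 480·f·(1 − s).
- Risk in those recorded as unexposed: pm = [480·f·s·p1 + 480·(1 − f)·0.5] / (480 − n1).
- Recorded OR = OR / [pm/(1 − pm)].

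Example with f = 10%, OR 2.5 and s = 20%: p1 = 0.714; n1 = 38.4; pm = (6.86 + 216)/441.6 = 0.505; recorded OR = 2.45.

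| f | True OR | Power, s = 0 | s = 5% | s = 10% | s = 20% | Recorded OR, s = 20% |
|---|---|---|---|---|---|---|
| 10% | 1.78 | 45.2% | 43.1% | 41.0% | 36.7% | 1.76 |
| 10% | 2.5 | 82.6% | 80.3% | 77.8% | 72.1% | 2.45 |
| 20% | 1.78 | 69.8% | 67.0% | 64.0% | 57.8% | 1.73 |
| 20% | 2.5 | 97.5% | 96.6% | 95.5% | 92.5% | 2.40 |

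At 5% out of school the loss is about 1 to 3 points. At 20% it is 5 to 12 points. The odds ratio itself moves little, because the main effect is that fewer participants are recorded as exposed. The illustration takes school status to be unrelated to outcome. If it is related, the distortion could be larger or differ in direction, and the documents give nothing to size it.

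**The case against.** The strongest reply is that most of each scale works for everyone. Six HFAQ items and four disability-index items do not depend on school. The listed exposure is a higher HFAQ level, and on a graded score 6 of 9 is still high. This stands, and it limits the damage to under-scoring rather than loss of the measure.

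Second, scoring and the handling of blanks belong to the analysis plan, which the protocol promises separately. This also stands for the scoring rule. It does not cover the missing answer option, because a plan cannot use information that was never collected. Weekly working hours on the follow-up form may hint at who has left school, but they are not a record of attendance and are not asked at baseline.

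Third, the questionnaire is to be pilot tested among 8- to 19-year-olds. Piloting might reveal the gap, but the forms as shown contain no remedy.

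Fourth, the objective defines exposures as those collected at recruitment, so participants who leave school later cannot distort a baseline exposure. This stands: the baseline form is what matters, and the follow-up form matters only for consistency.

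Finally, the job questions do not show that anyone is out of school, since a job can be held alongside it. They show only that working participants were foreseen.

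**Conclusion.** The point holds as a measurement problem. Four school-bound items in two named baseline exposures have no answer for a participant who is not at school, and school status is not recorded. If such participants answer No or leave blanks, their scores stop at 6 of 9 and 4 of 5, and this cannot be told from true absence of difficulty. The under-scoring depends on age and school status. Its size rests on the share out of school, which is not given, and the effect is small if that share is small.

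A reader might infer that these participants cannot reach the maximum HFAQ on which the study was sized, so that this category has no sensitivity in them. The documents do not support that. Nothing prevents a Yes, and maximum HFAQ is not defined in the text, so it could be a top category rather than all nine items. It is only one of four factors named in the first rationale, while the calculation shown in Appendix 5 models sex and sleep alone. The 480/504 follows from events per variable and does not change. The 17% and 33% are ceilings from counting year-groups, not estimates of who is out of school.

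**What to change.** On the baseline form, add the answer *I do not go to school / not applicable* to the three HFAQ items and the one disability-index item. Make the same change on the follow-up form for consistency. For participants who choose it, score each scale as the proportion of applicable items answered Yes: six of six rather than six of nine on the HFAQ, and four of four rather than four of five on the disability index. Keep the full-item score in pupils for comparison with the earlier studies. The scoring rule can sit in the analysis plan, but the answer option has to be on the form.

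The cost is one extra answer on four items and one scoring rule. The downside is that scores in participants out of school rest on fewer items, and the source instrument is slightly modified.

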The objective of this study is to investigate which descriptive patient variables (**exposures**) among 8-19-year-old children and adolescents with self-reported MSK pain (**population**), collected at time of recruitment, are associated to a higher risk of pain (**outcome**) at follow up.

FINER

F	Feasible	-Adequate no. of subjects: 500 -Technical expertise: N/A -Affordable in time and money: Time: short amount of time spent on recruitment per patient and recruitment executed by a GP employee or the GP. Money: a minimum cost per patient, according to rates by The Committee of Multipractice Studies in General Practice. -Manageable in scope: yes
I	Interesting	-Yes, high persistence of youth MSK pain and parental child pain acceptance
N	Novel	-Yes, lack of knowledge of prognostic factors in youth MSK pain and in the setting of general practice
E	Ethical	-Yes, approved by the National Ethics Committee (NVK)(28), without cause for further application.
R	Relevant	-To scientific knowledge: yes. -To clinical and health policy: yes. -To future research: yes.

Methods

Literature search to inform this study

Before commencing the planning of this cohort study, we conducted a systematic literature search to see if other prospective studies had investigated the same research question or were planning to do so. None specifically investigated childhood or adolescent prognostic factors for MSK pain in a general practice setting, nor did any of the included studies find any treatment effect modifiers(14). The systematic review in mention, has now been completed and this cohort study is based on the findings from that review. The prognostic factors found in our review, sparsely covered ethnicity, race, parental income, and residence, which will be investigated in this study. We furthermore limit our patient group to 8-19 years in order to preserve focus on an age group for which only limited knowledge on prognostic factors is available.

Design

This study is a prospective cohort study. We will use the STROBE guideline to report our study findings(29). Below is an illustration of the time line for our study process (figure 1), inspired by the guidelines of Prognosis Research, made by the PROGRESS Group(30). For validation of the prognostic screening, we will use the Transparent Reporting of a multivariable prediction model for Individual Prognosis Or Diagnosis (TRIPOD) Statement(31) and The TRIPOD Explanation and Elaboration document(32) (Appendix 4).

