(NVK) National Scientific Ethics Committee

Figure 1 Illustration of the timing of our study up to the point of publication and sharing of results.

Study setting

General practice clinics in Denmark.

Eligibility criteria for participation of participants and parents

Participants

The children and adolescents must have self-reported MSK pain at the time of recruitment and consult the GP in relation to their MSK pain. The primary reason for consultation may not necessarily be listed as MSK pain, but to be eligible for inclusion, MSK pain must be mentioned during the consultation with the GP. We do not have a pre-defined minimum or maximum MSK pain duration as a eligibility criteria and patients are eligible whether or not they have previously consulted their GP for their current MSK complaint.

We define MSK pain according to the International Association for the Study of Pain, IASP as: “pain arisen from muscle, tendon, bone, and joint”. Pain due to tumor, fracture, infection, or systemic and neurological cause will be excluded. Types of pain will be labelled according to the region affected, e.g. back pain, neck pain, shoulder pain, knee pain etc(33).

After consulting the GP in relation to MSK pain, inclusion and exclusion criteria will be applied as follows:

Inclusion criteria:

- 8 to 19 years
- Self-reported musculoskeletal pain

Traumatic pain caused by soft tissue damage, contusion or otherwise (excluding fracture), will be included.

Exclusion criteria:

- 0-7 or 20+ years
- Self-reported musculoskeletal pain due to tumor, fracture, infection, or systemic and neurological causes.

The inclusion and exclusion criteria will be determined at the following time-points:

1. During screening of the time schedule at the GP clinic
2. During the consultation with the GP
3. During a phone call made by the research assistant to either the participant or her/his parent, after retrieving their completed questionnaire from the GP clinic.

Parents

Parental participation will only be eligible after inclusion of their child. If a child is not eligible, or parental consent is not acquired on behalf of the child or adolescent <15 years of age, the parent will not be eligible for inclusion.

Declarations of consent

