The GP screens the schedule for the day, and indicates eligibility with the word **MSK** written next to the patient name.

When consulting a patient with the indicated **MSK**, the GP is reminded to hand the patient the patient material. This can be done, prior, during or in the end of a consultation while the patient is getting dressed.

The patient hands in the completed questionnaire to an employee of the clinic, who stores it in a locked place. NP or her assistant will collect this in agreement with the clinic.

It is also possible for the GP to include a patient if MSK pain comes up during the consultation, without prior mentioning and hence unknown by the employee.

We will recruit patients from September 2018 to December 2019 and expect 500 participants in the ChiBPS cohort. If we are not able to recruit the number of participants according to our sample size calculations recruitment will continue until this number is reached.

Recruitment of parents

The child must first be included in the study in order for his/her parent(s) to be eligible. For included children, we will also request data from parents during a time window of two weeks from the time of Part-Quest receipt. We are not selective as to if and how many of the parents wish to participate. Parents declining participation will not cause withdrawal of the child's eligibility or inclusion.

Contingency plan for recruitment

A tracking data base will be developed to facilitate tracking and accurate reminders to the clinics included. In the process of initial contact with the clinics, a number of expected included participants will be estimated by each clinic. The clinic will make this estimate based on its patient demography,

which can be different across clinics e.g. some clinics will have a majority of young patients and others the opposite. This number will indicate a minimum for successful recruitment.

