Hereafter, data will be extracted from REDCap and transferred to a table similar table 1, which will then be anonymized through participant ID.

Statistical methods

Descriptive results will be stratified by sex and MSK pain type, presented with their central estimate and appropriate measure of dispersion (95% confidence interval CI). All descriptive statistics and test will be reported in accordance to the recommendations of the STROBE statement(29).

We will test the univariate association between each potential prognostic factor as well as combining the factors in a multivariable model to show the individual contributions.

The primary analysis will be done on those who has a first time consultation with their GP concerning their current MSK pain, but all consultations will be included.

The full statistical analysis plan will be developed concurrently and will be finalized before the last patient is enrolled. We minimize information bias by using identical questionnaires for all patients included, e.g. by asking both Danes and non-Danes whether they feel Danish or not.

Ethics and dissemination

The Ethics Committee of the North Denmark Region has waived the need for ethical approval of this study (date 090617). The Multidisciplinary Committee has approved the study and recommends Danish GPs to participate (ID: MPU 20-2017 / date 100117). We are currently applying their grant, to provide compensation to the included GPs for every recruited participant they provide to the study. The Danish Data Protection Agency has similarly granted access to the project (date 101717). All mentioned reviews are executed prior to protocol registration in ClinicalTrials.gov and to enrollment of the first participant (figure 1).

The adolescents included in the ChiBPS cohort will receive usual care, i.e. as usually administered at their GP. This study will not intervene in the diagnostic and therapeutic process.

The manuscript will be submitted for publication in an appropriate peer-reviewed journal. In addition to this we will produce material for distribution among general practitioners and other healthcare providers managing children and adolescents with MSK pain. This will be done by data visualization through social media, websites and patient associations. The included participants will also be offered knowledge sharing of study results, if interested.

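### At the protocol's own 20 events per factor, 480 participants support 12 model parameters, not the top of the stated 10–15 range; and the figure of 125 cases per factor divides participants, not cases

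*Protocol*

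**What the plan says.** The Sample-size section of the protocol gives two rationales for about 500 participants and then an events-per-variable calculation.

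The second rationale takes 500 subjects, assumes that 50% (250) will be cases at the primary follow-up, and describes this as "giving approximately 125 cases per prognostic factor (500/number of prognostic factors"). The number of prognostic factors used as divisor is not given.

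The events-per-variable calculation again assumes 50% with pain at follow-up and sets the criterion that "20 events for each to be tested factor are needed". It continues: "The model should allow for 10-15 variables in a multivariable logistic regression analysis. This would lead to a sample size of 480". The allowance for loss follows: "Assumed, 5% is lost to follow-up and we have a sample-size of 504 included participants".

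Two other places bear on which participants the limit applies to. Under Statistical methods, the primary analysis is on those with "a first time consultation with their GP concerning their current MSK pain, but all consultations will be included". Under the eligibility criteria, "patients are eligible whether or not they have previously consulted their GP for their current MSK complaint".

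**The concern.** The event proportion and the events required per factor are both fixed, so each number of variables implies one sample size. A range of 10 to 15 variables should therefore produce a range of sample sizes, yet the section gives one figure and does not say which number of variables it belongs to. Whoever writes or runs the analysis could take 15 as covered at 20 events each, which it is not.

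The limit is a practical one. The exposure list and the questionnaires offer far more than 12 candidate factors, and several have more than two categories. The protocol counts variables, whereas an events-per-variable rule is used up by model parameters.

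The figure of 125 cases per factor is part of the stated reason for choosing 500. Its printed formula has participants in the numerator, while the result is labelled as cases.

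**Working it through.** **Inputs, all from the Sample-size section:** event proportion 0.50; 20 events per factor; 10–15 variables; 480 analysed; 5% loss; 504 included; 250 cases among 500 subjects; 125 cases per factor.

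**Step 1: reproduce the plan's figures.** For k parameters, N = 20 × k / 0.50 = 40k. With k = 12, N = 480, exactly as stated. Of the whole numbers from 10 to 15, no other gives 480. The allowance for loss also reproduces: 480 × 1.05 = 504.

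**Step 2: the whole stated range.** With 480 analysed there are 480 × 0.50 = 240 events.

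| Parameters k | N needed (40k) | Events per parameter at 480 (240/k) |
|---|---|---|
| 10 | 400 | 24.0 |
| 11 | 440 | 21.8 |
| 12 | 480 | 20.0 |
| 13 | 520 | 18.5 |
| 14 | 560 | 17.1 |
| 15 | 600 | 16.0 |

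The criterion is met for 10 to 12 and missed for 13 to 15.

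**Step 3: does the enrolled number leave slack?** 504 × 0.95 = 478.8 analysed; × 0.50 = 239.4 events; / 20 = 11.97. So the limit stays at about 12.

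**Step 4: parameters, not variables.** Pain-episode duration has four answer categories (Appendix 1, question 13), parental education five and household income four (Appendix 3, questions 14 and 15). If these were entered as unordered categories, which is an assumption because the protocol does not say how they will be coded, the three would use 3 + 4 + 3 = 10 parameters. A count of 12 holds for variables only if each takes one parameter.

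**Step 5: the 125 figure.** Let m be the unstated number of factors.

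- The printed formula is 500/m. It gives 125 only when m = 4. That is also the number of factors named in the first rationale (female sex, disability index, multisite pain, HFAQ).
- Cases per factor on the section's own count of cases are 250/m, half the printed formula for any m. With m = 4 this is 62.5.
- 250/m gives 125 only when m = 2. The second rationale does name two areas, ethnicity and socioeconomic status. But with m = 2 the printed formula would give 250.

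No value of m makes the formula, the label and the number all correct.

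**The case against.** The strongest reply is that 12 lies inside the range, close to its midpoint of 12.5, and gives 480 exactly. On that reading the authors quoted an approximate range and sized at a sensible value within it. This stands in part: 480 is not a miscalculation, and a reader who infers that the sample size is wrong, or that more participants must be enrolled, goes beyond the text. The section does not state that 480 supports 15 variables at 20 events each. What remains is that the planning value is undisclosed and the upper part of the printed range fails the printed criterion.

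The consequence is also moderate. At 15 parameters there are 16 events each instead of 20, the section calls the results exploratory, and 500 has a separate rationale based on expected P-values. This limits the weight of the point but does not make the statement right.

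On the 125 figure, a reader might infer that the number of cases is overstated twofold. That follows only if four factors were meant. With two, the number is right and only the numerator in the parenthesis is a slip. What is established is that formula and label disagree.

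A reader might also infer that the primary analysis supports fewer than 12 parameters because it concerns first-time consulters. The documents do not establish this. The share of first-time consulters is not given, the sentence under Statistical methods also includes all consultations, and the model population may be set in a statistical analysis plan that is not at hand. It can be raised only as a condition.

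Finally, a reader might make something of "Adequate no. of subjects: 500" and "expect 500 participants in the ChiBPS cohort" against the calculated 504. This is immaterial: the recruitment section says that enrolment continues until the calculated number is reached.

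**Conclusion.** The point holds as an inconsistency in the stated basis for the sample size, not as an error in the sample size. On the protocol's assumptions of 50% events and 20 events per factor, 480 analysed participants (240 events) support up to 12 model parameters. At 13 to 15 the events per parameter fall to between 18.5 and 16.0, which is 7.7% to 20% below the protocol's own criterion (1.5/20 with unrounded 18.46 giving 1.54/20 = 7.7%; 4/20 = 20%).

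Separately, the formula for cases per factor divides participants. The intended value is 62.5 if there are four factors and 125 if there are two; the text does not show which.

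The first conclusion rests on the 50% event proportion being realised and on counting parameters. The second needs no assumption beyond the section's own count of 250 cases. The correction is worth making because it concerns the stated justification and costs very little.

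**What to change.** In the Sample-size section, do one of the following:

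- replace the range of 10–15 variables with: *up to 12 model parameters (about 240 events among 480 analysed, 20 events per parameter; a factor with more than two categories uses more than one parameter)*; or
- keep 15, counted as parameters, and state that the criterion is then 16 events per parameter.

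In the sentence on 125 cases, state the number of prognostic factors. Then either use 250 as the numerator and give the resulting number of cases, or keep 500 as the numerator and label the result as participants.

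Optionally add a conditional note: if the multivariable model is confined to first-time consulters and repeat consulters are enrolled, the limit is the number of events in that group divided by 20.

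The cost is a few sentences of text. No change to recruitment or data collection is required.
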